**Analysis and Statistics:**

All data were analyzed using IBM SPSS Statistics version 26.0 for Windows. Prior to selecting appropriate statistical tests for continuous variables, the Shapiro-Wilk test was conducted to assess the normality of data distribution. For variables exhibiting a normal distribution, independent samples t-tests or paired samples t-tests were applied. For non-normally distributed data, the Mann-Whitney U test or the Wilcoxon Signed Rank test was used instead. Treatment outcomes were assessed by comparing post-intervention time points with baseline measurements.

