**Methods:**

A crossover randomized controlled trial design was used. We recruited adult patients with ischemic or hemorrhagic stroke for more than 3 months, who were able to walk independently with or without device on level ground, but presented with spasticity of the knee extensor muscles. And randomly assigned to either an early injection group or a delayed injection group. Both groups received six weeks of exoskeleton robot-assisted gait training one week after injection (2–3 sessions per week, 40 minutes per session, for a total of 12 sessions) and were followed up at three months post-training. The injection site was then switched. The data were

combined according to whether the rectus femoris was injected: injection group (Group A) and non-injection group (Group B). The primary outcome was knee kinematics, including knee flexion angle and range of motion. Secondary outcomes included muscle strength, muscle tone, functional walking ability (6MWT, mEFA), balance (BBS), and self-efficacy (ABC, NEADL).

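### No test is assigned to injected versus non-injected, and none of the four listed, applied to that pooled contrast, both keeps the crossover pairing and adjusts for period

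*Combined protocol and SAP*

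**What the plan says.** The Methods section of the combined protocol and SAP states: "A crossover randomized controlled trial design was used". Patients form two sequences: "And randomly assigned to either an early injection group or a delayed injection group". Both receive the robot training and a three-month follow-up, after which "The injection site was then switched". Data from the two periods are then pooled by injection status into Group A (injected) and Group B (not injected).

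The Analysis and Statistics section gives one rule for choosing a test: "Prior to selecting appropriate statistical tests for continuous variables, the Shapiro-Wilk test was conducted to assess the normality of data distribution". After that, "For variables exhibiting a normal distribution, independent samples t-tests or paired samples t-tests were applied", and "For non-normally distributed data, the Mann-Whitney U test or the Wilcoxon Signed Rank test was used instead". The only comparison it describes is this: "Treatment outcomes were assessed by comparing post-intervention time points with baseline measurements". It names no period, sequence or carryover term and no mixed model.

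**The concern.** The aim is the effect of adding rectus femoris injection to robot training. Both randomised groups are trained, so change from baseline within one group cannot isolate the injection. Only A versus B can, and no test is assigned to it.

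Normality testing separates t-tests from rank tests. It says nothing about paired or unpaired, so that choice stays open. The unpaired tests, applied to A versus B, treat one patient's two results as coming from two people. The paired tests avoid this but do not remove a period effect. Such an effect is a real possibility, because everyone has had a course of training and months of follow-up before the second period begins.

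The plan also leaves open whether baseline means study entry or the start of each period. This matters because the correlation between a patient's two results depends on it. At stake are the precision that the crossover was meant to buy and, if the completed sequences differ in size, the estimate itself.

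**Working it through.** **Inputs.** From Methods: crossover, two sequences, allocation ratio not stated, pooling by injection status. From Analysis and Statistics: the four tests. The documents give no sample size, alpha, power, SD, correlation or period effect, so there is no planned figure to reproduce. Everything below assumes two-sided 5% testing and the stated values of the unknowns.

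**1. Unpaired test of A versus B.** Let N patients complete both periods, with outcome SD s and within-patient correlation rho.

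- True variance of the mean A−B difference: 2s²(1−rho)/N.
- Variance the unpaired test uses: 2s²/N.
- SE ratio: 1/√(1−rho).
- Power, when a paired test has 80%: P(Z > 1.96/√(1−rho) − 2.80).

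| Assumed rho | SE ratio | Power, formula | Simulated, N=20 | Simulated, N=40 |
|---|---|---|---|---|
| 0 | 1.00 | 80.0% | 82.3% | 81.1% |
| 0.3 | 1.20 | 67.7% | 70.1% | 69.1% |
| 0.5 | 1.41 | 51.2% | 54.2% | 52.5% |
| 0.7 | 1.83 | 21.9% | 26.6% | 24.0% |

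(40,000 simulated t-tests per cell.)

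With positive rho the test is conservative, so false positives do not rise. With negative rho, type I error is 2·P(Z > 1.96/√(1−rho)), which is 5.58% at −0.05 and 6.17% at −0.10. A rho near 0 is plausible if the outcome is change from a period-specific baseline, and then little is lost.

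**2. Plain paired test, equal sequences.** A period effect of p (in SDs of the within-patient difference) shifts A−B by +p in one sequence and −p in the other. The mean is unaffected, but the estimated SE grows by √(1+p²). At p = 0.5 this is √1.25 = 1.118, and power is P(Z > 1.96 × 1.118 − 2.80), about 73%. Simulation gives 72.6% for the plain paired test at both N=20 and N=40, against 79.8% and 80.0% with period adjustment.

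**3. All three analyses together.** Simulated power with 20 patients split 10:10, outcome SD 1, true effect 0.5 SD, no carryover, and 20,000 runs per row. Here the period effect is in outcome SDs.

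| rho | Period effect | Unpaired | Paired | Period-adjusted |
|---|---|---|---|---|
| 0.5 | 0 | 0.280 | 0.568 | 0.565 |
| 0.5 | 0.5 | 0.258 | 0.472 | 0.568 |
| 0.5 | 1.0 | 0.185 | 0.255 | 0.566 |
| 0.8 | 0 | 0.215 | 0.918 | 0.916 |
| 0.8 | 0.5 | 0.176 | 0.791 | 0.914 |
| 0.8 | 1.0 | 0.097 | 0.350 | 0.917 |

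The period-adjusted test holds type I error at about 0.05 in every setting.

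**4. Unequal completed sequences.** The period effect no longer cancels. The size of the bias in the mean A−B difference is period effect × |n1−n2|/N. For a 1 SD period effect this is 4/20 = 0.20 SD at 12:8 and 8/20 = 0.40 SD at 14:6. Type I error of the paired test is 0.163 (rho 0.5) and 0.202 (rho 0.8) at 14:6. At 12:8 it is below 5% (0.028 and 0.012), because the inflated SE outweighs the bias.

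The rank tests were not simulated. By construction, Mann-Whitney U on the pooled groups drops the pairing and Wilcoxon signed rank does not adjust for period.

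**The case against.** The strongest reply is that this is a gap in specification and not a demonstrated error. Paired tests are on the list, and a competent analyst could use them for A versus B and keep the unpaired tests for comparing the randomised groups. Nothing shows that unpaired tests of A versus B are intended. This stands, and the larger power losses apply only if they are used that way.

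A second reply is that the listed independent t-test or Mann-Whitney U would be valid if applied to within-patient period differences, compared between the early and delayed sequences. This is correct for completers. But the plan does not describe that analysis. It describes pooling by injection status, which is a different comparison.

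A third is that the sizes are hypothetical. This also stands: every unknown is assumed, most of the error is on the conservative side, and the bias in step 4 needs both a period effect and unequal completed sequences.

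None of this supplies a test for the main contrast, and the paired reading still leaves period unadjusted.

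**Conclusion.** The concern holds and should be fixed. The plan assigns no test to its main contrast. Each listed test, applied to the pooled groups, either drops the pairing or ignores period. The consequence runs from almost nothing (rho near 0, or a paired test with no period effect) to a large loss of power (about 22% instead of 80% for an unpaired test at rho 0.7). Bias is possible if completed sequences are unequal. These figures illustrate the mechanism under assumed values and are not properties of this trial. Confidence is medium, because the documents do not show which reading was meant.

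**What to change.** State one analysis for A versus B that keeps the pairing and adjusts for period. Either of these will do:

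- A linear mixed model with treatment, period and sequence as fixed effects and patient as random effect.
- For completers, each patient's period 1 minus period 2 difference, compared between the two randomised sequences by t-test, or by Mann-Whitney U if non-normal. With treatment effect τ and period effect π, the sequence means are τ−π and −τ−π. Half their difference is τ, free of π. This assumes no carryover.

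Name the time point, say whether baseline is study entry or period start, and report the A−B estimate with a 95% CI. Keep unpaired tests only for comparisons between the randomised sequences.

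The Participants section speaks of recruitment in the future, while Methods and Analysis and Statistics are in the past tense. If the data have already been analysed, report the new work as a re-analysis and label it as not pre-specified.

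The cost is a few lines of SAP wording and a little work in SPSS 26, with no extra patients or visits.

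### The analysis section names only a post-versus-baseline comparison and assigns no test to the injected versus non-injected contrast that the crossover was set up to give

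*Combined protocol and SAP*

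**What the plan says.** Methods sets up the contrast. It states "A crossover randomized controlled trial design was used", with randomisation to early or delayed injection, and says that the data were "combined according to whether the rectus femoris was injected: injection group (Group A) and non-injection group (Group B". On treatment and follow-up it says "Both groups received six weeks of exoskeleton robot-assisted gait training one week after injection" and that the groups "were followed up at three months post-training". It then adds "The injection site was then switched". For the endpoint, "The primary outcome was knee kinematics, including knee flexion angle and range of motion". No primary time point is given.

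Analysis and Statistics uses a Shapiro-Wilk test to choose between parametric and rank methods. For normal data, "independent samples t-tests or paired samples t-tests were applied". For other data the Mann-Whitney U or Wilcoxon signed-rank test is used. The section closes with its only named comparison: "Treatment outcomes were assessed by comparing post-intervention time points with baseline measurements".

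**The concern.** The Aim is the effect of combining rectus femoris injection with robot training. Methods gives the training to both the early and the delayed group. A patient's change from baseline therefore contains the training effect, anything that alters with time, and the injection effect if there was one. A significant change in Group A would look the same whether training or injection produced it.

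The comparison that could separate them is A against B. No sentence says that it will be made, by which test, on post values or on changes, for which knee measure, or when. The one selection rule, normality, divides t-tests from rank tests. It does not divide independent from paired tests, which is the choice that matters in a crossover. Measure, time point and test could all be settled after the data are seen.

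**Working it through.** The documents give no sample size, significance level, effect size or correlation, so there is no figure of the plan's to reproduce. The check has two parts.

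**1. What the named comparison can identify.** Write the expected change in a period as T (training) + S (time and other influences) + I (injection, if given).

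- Change from baseline in A: T + S + I.
- Change from baseline in B, if B has the same training: T + S.
- A minus B: I.

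With S = 0, the change in A is 0.5 SD if T = 0.5 and I = 0, and also if T = 0 and I = 0.5. The named comparison cannot tell these apart.

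**2. Why the choice of test for A versus B matters.** All inputs are assumed: n = 20, 30 or 40 patients, half in each sequence, each measured under both conditions; change SD 1 in each period; training gain 0.5 SD in both periods; injection effect 0.5 SD (or 0 for the null); within-patient correlation ρ between the two changes; two-sided 5%; no carryover.

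- True standard error of mean A minus mean B: √(2(1−ρ)/n).
- Standard error that the independent test uses: about √(2/n).
- Ratio, used to true: 1/√(1−ρ).
- Null rate favouring A: about Φ(−1.96/√(1−ρ)), against a nominal 2.5%.

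Substituting:

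- ρ = 0.5: 1.96/0.707 = 2.77, so about 0.3%.
- ρ = 0: 1.96/1 = 1.96, so 2.5%.
- ρ = −0.5: 1.96/1.225 = 1.60, so about 5.5%.

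Simulation agrees. Power is shown as independent test / crossover test (period differences compared between sequences), accurate to about one percentage point:

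| ρ | n = 20 | n = 30 | n = 40 | Null rate favouring A, independent test |
|---|---|---|---|---|
| 0.7 | 25 / 78% | 46 / 93% | 67 / 98% | 0.02-0.05% |
| 0.5 | 29 / 56% | 47 / 75% | 64 / 87% | 0.3-0.4% |
| 0.3 | 31 / 43% | 47 / 61% | 62 / 74% | 1.0-1.1% |
| 0 | 33 / 31% | 48 / 47% | 60 / 58% | about 2.5% |
| −0.5 | 37 / 23% | 48 / 33% | 59 / 43% | about 5.5% |

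The crossover test favours A in about 2.5% of null trials in every row. The independent test's higher power at ρ = −0.5 comes with an inflated error rate, so it is not a real advantage.

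Most of the gain at positive ρ comes from pairing. At ρ = 0.5 a plain paired t-test has 56%, 75% and 87% power, the same as the crossover test. If the training gain drops to 0.2 SD in period 2, the plain paired test falls to 53%, 72% and 85%, while the crossover test with its period term stays at 56%, 75% and 87%.

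**The case against.** The strongest reply is that an A-versus-B test is the natural reading. Pooling by injection status has little other use, two-sample tests are listed, and the last sentence may define the quantity analysed (change from baseline) rather than the only contrast. That is a fair reading. A reader might infer that only pre-post tests will be run, and the documents do not support that inference. What stands is that no sentence commits to the contrast.

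A reader might also infer that both conditions receive the same training in both periods. Methods says this of the early and delayed groups, before it mentions the switch. It never says that training or kinematic assessment is repeated afterwards. Equal training in part 1 and measurement in both periods in part 2 are therefore assumptions.

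Nor can one say that the independent test is always conservative or always much weaker. The correlation here is between changes and need not be positive. With separate baselines and independent errors around a stable patient level it is 0. If one measurement ends period 1 and also starts period 2, it can be negative. The documents do not say which baseline applies, so the direction of the error is open.

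Finally, Participants speaks of recruitment in the future tense, while Methods and the analysis section are mostly in the past. If the analysis is already done, any new specification is post hoc.

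**Conclusion.** The point holds as a missing commitment and should be fixed. The one comparison named cannot isolate the injection effect, and the contrast that could is assigned no test, measure or time point.

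The finding itself rests on the text alone. Its numerical size rests on the assumed inputs. At correlation 0.5 the choice between listed approaches moves power from about 29-64% to 56-87%. At 0 it hardly matters. At −0.5 the independent test roughly doubles the rate of false findings in favour of A (about 5.5% against 2.5%). Only an analysis that keeps the pairing holds its error rate across this range, provided that there is no differential carryover and that kinematics are measured in both periods.

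**What to change.** For the primary outcome, replace the test-selection sentences and the closing sentence of Analysis and Statistics with:

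> The primary comparison is the within-patient difference between the rectus femoris-injected and non-injected conditions in change from the start-of-period baseline in [one named knee kinematic measure] at [one named post-training time point]. It is estimated with a 95% CI from a paired crossover analysis with a period term. If the differences are clearly non-normal, the rank version is used (period differences compared between sequences). The estimate assumes no differential carryover. Within-condition changes from baseline are descriptive only.

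Separately, reconcile three statements in Methods: training is timed from an injection in both groups, the injection site is later switched, and Group B is called a non-injection group. State what the non-injected condition is, and whether training and kinematic assessment are repeated after the switch. The paired analysis depends on kinematics being measured in both periods. If the data have already been analysed, report the change as a labelled post hoc one.

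The cost is a slightly more complex analysis, one measure and one time point fixed as primary, and within-group gains no longer available as evidence for the injection. The no-carryover assumption is a real limitation: a carryover of c in the period-2 change of patients injected first would bias the estimate by −c/2. Whether extra visits are needed cannot be judged, because the documents give no assessment schedule for the second period.

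### Only covariate-free tests against baseline are planned; if Groups A and B are contrasted on changes, the variance is between 1 and 2 times that of a baseline-adjusted contrast

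*Combined protocol and SAP*

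**What the plan says.** The Methods section states "A crossover randomized controlled trial design was used", with patients randomised to early or delayed injection. On timing, both groups "were followed up at three months post-training. The injection site was then switched". The data are then "combined according to whether the rectus femoris was injected: injection group (Group A) and non-injection group (Group B"). On the endpoint: "The primary outcome was knee kinematics, including knee flexion angle and range of motion".

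The Analysis and Statistics section gives the tests. For normally distributed variables, "independent samples t-tests or paired samples t-tests were applied"; for the others, "the Mann-Whitney U test or the Wilcoxon Signed Rank test was used instead". It closes with "Treatment outcomes were assessed by comparing post-intervention time points with baseline measurements".

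The document leaves three things open:
- whether A and B are contrasted on changes, on post values, or not directly at all;
- which visit is the baseline for the second period;
- any SD, correlation, sample size, alpha or power.

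**The concern.** Baseline enters the plan only as something to compare against. No ANCOVA, mixed model or other analysis with a covariate is named. Forming two groups, listing two-sample tests and judging outcomes against baseline together suggest an A-versus-B test on changes. Such a test fixes the weight on baseline at 1. A covariate analysis estimates that weight from the data and, apart from the degree of freedom it uses, cannot do worse in large samples.

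The trial asks what the injection adds to training that both groups receive, and it states no sample size, so avoidable loss of precision matters. The order of visits raises a second issue. The switch comes after the three-month visit, so that visit might serve both as the first-period outcome and as the second-period baseline. Subtraction would then use one measurement in two roles.

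**Working it through.** The plan has no figure to reproduce. All correlations below are assumptions, and SDs are taken as equal at every visit unless stated.

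**1. Crossover, separate baseline in each period.** Let r1 be the baseline-post correlation within a period and r2 the correlation between measurements in different periods. Per patient, in units of SD²:
- A minus B on post values: 2(1−r2). The baseline difference has the same variance, and the covariance of the two differences is 2(r1−r2).
- A minus B on changes: 2(1−r2) + 2(1−r2) − 4(r1−r2) = 4(1−r1).
- A minus B adjusted for the baseline difference: 2(1−r2)(1−rho²), with rho = (r1−r2)/(1−r2).
- Since 4(1−r1) = 4(1−r2)(1−rho), the ratio of changes to adjusted is 2/(1+rho).

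| r1 / r2 | rho | Changes | Post only | Adjusted | Changes ÷ adjusted |
|---|---|---|---|---|---|
| 0.7 / 0.7 | 0 | 1.20 | 0.60 | 0.60 | 2.00 |
| 0.6 / 0.5 | 0.20 | 1.60 | 1.00 | 0.96 | 1.67 |
| 0.8 / 0.7 | 0.33 | 0.80 | 0.60 | 0.53 | 1.50 |
| 0.8 / 0.6 | 0.50 | 0.80 | 0.80 | 0.60 | 1.33 |
| 0.9 / 0.7 | 0.67 | 0.40 | 0.60 | 0.33 | 1.20 |
| 0.9 / 0.6 | 0.75 | 0.40 | 0.80 | 0.35 | 1.14 |

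With correlation decaying over time (0.7 to 0.95 per month, assumed visits at 0, 1.6, 4.6 and 6.2 months), the ratio is 1.24 to 1.41.

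**2. Pooled groups treated as independent.** Changes have variance 2(1−r) and ANCOVA 1−r², so the ratio is again 2/(1+r): 1.54 at r = 0.3, 1.33 at 0.5, 1.18 at 0.7, 1.11 at 0.8 and 1.05 at 0.9. A simulation with 20 per arm gave 1.96, 1.30 and 1.08 at r = 0, 0.5 and 0.8, against 2.00, 1.33 and 1.11 from the formula.

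**3. One study baseline x for both periods.** (yA−x) − (yB−x) = yA−yB. The baseline cancels and the ratio is 1.0.

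**4. Three-month visit also used as second-period baseline.** Let y1 be the study baseline, and y2 and y4 the three-month values of periods 1 and 2.
- The difference in changes is (y2−y1) − (y4−y2) = 2·y2 − y1 − y4.
- With equal correlations r its variance is 4+1+1 + 2(−2r−2r+r) = 6(1−r), against 2(1−r) for y2−y4. The ratio is 3; at r = 0.7, 1.80 against 0.60.
- The expectations can also differ. Suppose the injection shifts its own period's three-month value by τ, with no carryover into y4. Period effects cancel when the two sequences are averaged. Patients injected first contribute 2τ to the A-minus-B change contrast and those injected second contribute τ, an average of 1.5τ, whereas the plain difference gives τ.

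**The case against.** The strongest objection is that the sentence on baseline may describe within-group before-and-after tests only, in which case there is no A-versus-B contrast on changes to criticise. That stands as a matter of text: the change contrast is an inference. It does not remove the need for action. Both groups receive the same robot training, so within-group tests alone would not isolate the injection, and the contrast would still have to be stated.

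A reader might also infer that the plan loses a factor of 2 to 3. The document does not support that. A factor of 2 in the crossover needs visits within a period to correlate no better than visits in different periods. The factor of 3 needs a change contrast, the three-month visit, that visit reused as baseline, and equal correlations. Even then it compares quantities that may have different expectations.

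Nor does subtraction always add noise. Against post values alone it lowers the variance whenever r1 > (1+r2)/2, as at 0.9/0.7 (0.40 against 0.60), and it breaks even at 0.8/0.6. The gain claimed here is over the contrast on changes and comes from the covariate. Once baseline is in the model, analysing post values or changes gives the same treatment estimate.

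Two further objections stand and shape the remedy. The second-period baseline follows randomised treatment, so adjusting for it can bias the contrast if the first-period effect persists. And if the pooled groups are tested as independent, the larger fault is ignoring the pairing and the period, which a covariate alone does not repair.

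**Conclusion.** The concern holds in a limited form. The planned tests cannot use baseline as a covariate, and a contrast of A with B on changes would generally be less precise than an adjusted one. The variance ratio is 2/(1+rho), between 1 and 2 for rho of 0 or more. Over the assumed crossover correlations it is 1.14 to 2.0, which corresponds to 14% to 100% more patients for the same precision.

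This rests on an inferred change contrast, separate period baselines (or pooled groups), equal SDs, and correlations that the document does not report. Equal SDs matter for the ceiling: in the pooled-group form, a baseline SD 1.41 times the post SD at r = 0 gives 2.99, but nothing in the document suggests such a gap. With one study baseline and a within-patient contrast, subtraction causes no loss.

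Change-score analysis with properly defined baselines is valid in a randomised trial, so with separate or common baselines this is a matter of efficiency. The exception is a shared three-month visit, where subtraction could also change what is estimated. A reader might conclude that a real injection effect will be missed; without a sample size, SD or effect size, that cannot be shown.

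**What to change.** 1. State the A-versus-B contrast and make it a within-patient crossover analysis with period, sequence and baseline. One form is ANCOVA of the within-patient period difference (period 1 minus period 2) on sequence plus the corresponding baseline difference. The intercept carries the period effect, and half the sequence contrast is the injection effect. An equivalent mixed model would also serve.
2. State which visit is the baseline for each period. If a single study baseline serves both, the baseline difference is zero and the term drops out of the ANCOVA.
3. If the second-period baseline is the first-period three-month visit, compare the three-month values within patient without subtracting it.
4. Because the second-period baseline follows randomised treatment, show the contrast with and without the covariate.
5. Keep comparisons of post values with baseline as description only.

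The cost is new analysis wording, about 1 degree of freedom and one extra sensitivity analysis. The plan already refers to baseline measurements. Whether a separate second-period baseline is recorded is not stated and should be confirmed first.
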